### **1 OBJECTIVES AND PURPOSE**

The study is being conducted to evaluate the safety and performance of fractional RF for the treatment and revision of stretch marks. Total expected duration of the clinical investigation is ten months (enrolment period of 2 months, study participation period of 8 months), while individual subject participation will take 8 months.

### **2 STUDY DESIGN AND ENDPOINTS**

#### **2.1 DESCRIPTION OF THE STUDY DESIGN**

This is a prospective, single centre, evaluator-blind study of the performance of fractional radiofrequency (RF) for the treatment and revision of stretch marks.

##### **2.1.1 PRIMARY ENDPOINT**

- Objective volumetric evaluation of striae via Antera 3D Imaging System Analysis at 12 and 16 weeks post-final treatment
- Improvement in the appearance of stretch marks at 12 weeks and 16 weeks post-treatment compared to baseline as assessed by investigator and blinded evaluators by photographic assessment utilizing the Global Aesthetic Improvement Scale (GAIS)

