##### **2.1.2 SECONDARY PERFORMANCE ENDPOINTS**

- Improvement in the appearance of stretch marks at 12 weeks and 16 weeks post-treatment compared to baseline as assessed by investigator utilizing the Modified Manchester Scar Scale (MSS)
- Subjects' assessment of satisfaction with the treatment using a Subject Satisfaction Scale at 12 weeks and 16 weeks post-treatment.

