## 4 INVESTIGATIONAL DEVICE

### 4.1 INVESTIGATIONAL DEVICE AND CONTROL DESCRIPTION

#### 4.1.2 DEVICE SPECIFIC CONSIDERATIONS

- Device model(s): Venus Viva™
- Device settings and programming: Ablation or Coagulation Mode; 180-280 volts, 5-30 ms pulse duration
- Duration of exposure and frequency: Multiple passes, 4 treatments, roughly 4-6 weeks apart, multiple treatment areas per subject may be treated. Treatment area size – 3"x3" or smaller

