### 4.3.2 ENROLLMENT/BASELINE/TREATMENT VISITS

#### **Visit 2 – Enrollment/Baseline/Treatment 1 Visit (Day 0)**

The investigator will confirm that the subject still meets the inclusion/exclusion criteria. This Baseline visit includes the first of the four treatments. In addition to the treatment, concomitant medications, photographs and the pain VAS and Tolerability Scale are to be completed by the patient. Investigator to assess immediate and short term response and complete a Modified Manchester Scar Scale (MSS) assessment.

Photographs will be taken prior to first treatment and throughout the study according to specified time points detailed in the Schedule of Events Table utilizing the Antera 3D Imaging System.

A topical anesthetic may be prescribed and applied to the treatment site prior to treatment at the investigator's discretion. The parameters may be modified during subsequent visits, as per the practitioner's discretion.

The investigator will examine the treated areas and report immediate and short term response (20-30 minutes post-treatment) using a 5-point scale. The assessment of discomfort/pain based on the subject's completion of the 10 cm VAS should also be documented immediately after each treatment.

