#### **Visit 5 – Treatment 4 - Week 12 (+/- 7 days)**

The Subject is to return to the clinic for the fourth and final treatment. In addition to the treatment, concomitant medications, photographs, AEs and the pain VAS and Tolerability Scale are to be completed by the patient. Investigator to assess immediate and short term response.

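### Protocol section 2.1.1 puts four to six results under one primary heading with no lead result, and lets the unblinded investigator's GAIS count as primary alongside the blinded rating

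*Protocol*

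**What the plan says.** The Protocol's heading is singular, "2.1.1 PRIMARY ENDPOINT", but two bullets follow it. The first reads "Objective volumetric evaluation of striae via Antera 3D Imaging System Analysis at 12 and 16 weeks post-final treatment". The second is improvement in appearance against baseline at the same two follow-up times, "as assessed by investigator and blinded evaluators by photographic assessment utilizing the Global Aesthetic Improvement Scale (GAIS". Neither bullet is placed ahead of the other, neither time point is placed ahead of the other, and the two kinds of GAIS rater are joined without an order.

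Section 2.1 describes the design: "This is a prospective, single centre, evaluator-blind study of the performance of fractional radiofrequency (RF". No comparator is described anywhere in the document. Section 3.1 sets enrolment to continue until 15 subjects have been treated.

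Section 4.3.2 gives the investigator an assessment role at every treatment. At Visit 2, "The investigator will examine the treated areas and report immediate and short term response"; Visits 3, 4 and 5 repeat the task ("Investigator to assess immediate and short term response"). Section 4.3.3 then has the investigator complete GAIS at Visit 6 (12 weeks) and Visit 7 (16 weeks). Photographs are scheduled at both of those visits.

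**The concern.** A primary endpoint should say in advance which result decides the question. Here three choices are left open within the primary set: instrument, time point and, for GAIS, rater. If volumetry and GAIS disagree, or 12 and 16 weeks disagree, or the investigator and the blinded evaluators disagree, section 2.1.1 does not say which result the performance conclusion follows.

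The rater is the sharpest part. In a before-and-after study with no described comparator, blinded rating is the main protection against expectation bias in a judgement of appearance. Section 2.1 advertises that protection, but section 2.1.1 gives primary standing to a rating made without it. As written, a favourable investigator GAIS could be reported as a primary result of an evaluator-blind study even if the blinded GAIS were not favourable.

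**Working it through.** The protocol gives no figure to reproduce on this point. The check is a count, followed by a comparison of sections.

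**Count of primary results** (inputs from section 2.1.1: 2 instruments, 2 time points, 2 kinds of GAIS rater)

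- GAIS raters taken as one assessment: 2 instruments x 2 time points = 4 results. Of these, GAIS at 12 weeks and GAIS at 16 weeks include the investigator's rating: 2 of 4.
- GAIS raters taken separately: (1 Antera + 2 GAIS rater types) x 2 time points = 6 results. Of these, the investigator's GAIS at 12 and at 16 weeks stand on the investigator alone: 2 of 6.

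The text does not settle which count is meant, so both are carried forward. On either count, no result is marked as leading.

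**Is the investigator's GAIS blind?**

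1. Section 2.1.1 names the investigator and the blinded evaluators as different raters and attaches the word for blinding only to the second. On the document's own wording, the investigator is not one of the blinded raters.
2. Section 4.3.2 has the investigator assess response at each of the four treatments (Visits 2 to 5). The investigator therefore knows that the subject was treated and how the skin reacted.
3. Section 4.3.3 has the investigator complete GAIS at the 12-week and 16-week visits. That the investigator then knows the assessment is post-treatment is an inference from the schedule, but a safe one.

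Steps 1 to 3 agree: the investigator's GAIS is an unblinded rating. Setting this beside section 2.1 (evaluator-blind) and section 2.1.1 (investigator's GAIS listed as primary, with no precedence for the blinded rating) gives the finding.

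**After the change proposed below:** 1 lead result + 3 supportive results (the rest of Antera and blinded GAIS at 12 and 16 weeks) + 2 secondary results (the investigator's GAIS at 12 and 16 weeks) = 6. Every result is still collected and reported; only its rank changes.

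**The case against.** The best defence has three parts.

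*The analysis plan may settle it.* A SAP may exist and is not shown. How several primary results are combined, and whether all must succeed, is commonly placed there. That part stands: the lack of a testing or success rule in the protocol is not held against it. But which measures and raters are primary is fixed in section 2.1.1 itself, and that designation is what is at issue.

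*Several primary measures are a permissible design.* This is true. It is a small single-centre study, and all results can be reported side by side, where a disagreement between raters would be visible. This lowers the stakes, but it does not say which rating carries the conclusion when they disagree.

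*Equal rank is inferred.* The protocol never states in words that the two raters rank equally. What can be said is that both sit in one primary bullet and neither is given precedence.

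A reader might also infer more than the documents support:

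- *That the performance conclusion rests solely on these results.* It does not: section 2.1.2 adds the Modified Manchester Scar Scale and subject satisfaction at the same follow-up times.
- *That the protocol is inconsistent because the investigator's scar-scale rating ("compared to baseline as assessed by investigator utilizing the Modified Manchester Scar Scale (MSS") is secondary while the investigator's GAIS is primary.* These are different instruments, and nothing ties the lower rank to the rater being unblinded.
- *That the false-positive rate is inflated by a known amount.* At an assumed 0.05 per independent test, 1 - 0.95^4 = 0.1855 and 1 - 0.95^6 = 0.2649. The protocol states no test or alpha, and the results would be correlated, so these figures describe an assumption and not this trial.
- *That no blinded GAIS is really planned, because section 4.3.3 names only the investigator.* Section 2.1.1 bases the evaluation on photographs, which are scheduled at both visits, so the blinded rating can be made away from the clinic.

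**Conclusion.** The point holds as an avoidable ambiguity in the primary endpoint, with a specific bias risk inside it. Section 2.1.1 lists four results, or six with GAIS raters counted separately, and designates no lead. Two of them are, or include, an unblinded rating in a study described as evaluator-blind.

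The conclusion rests on the wording of sections 2.1 and 2.1.1, on the visit schedule in sections 4.3.2 and 4.3.3, and on the inference that an investigator who assesses response at every treatment knows which assessments come afterwards. It does not depend on any assumed alpha, effect size or correlation. The documents do not show which instrument or visit ought to lead, so that choice belongs to the sponsor. This is a change worth making because it reduces bias at little cost; the text does not show that the study cannot be interpreted.

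**What to change.** Three edits to the protocol, made before any outcome is examined:

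1. In section 2.1.1, make the blinded evaluators' photographic GAIS the only primary GAIS rating.
2. Move the investigator's GAIS at 12 and 16 weeks to section 2.1.2 as a secondary endpoint.
3. In section 2.1.1, designate one lead instrument and one time point from those already listed, and label the other Antera and blinded GAIS results as supportive. The choice is the sponsor's.

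The cost is protocol wording. No visit, photograph or rating is added, since all of them are already planned. The downside is that fewer results can be called primary, and choosing one instrument and visit to lead puts the others in a supporting role.

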### 3 STUDY ENROLLMENT AND WITHDRAWAL

#### 3.1 STUDY POPULATION

The study will enroll male and female adult subjects requesting fractional radiofrequency treatment of stretch marks until 15 subjects have been treated according to the study protocol.

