#### **Visit 3 – Treatment 2 - Week 4 (+/- 7 days)**

The Subject is to return to the clinic for their second treatment. In addition to the treatment, concomitant medications, photographs, AEs and the pain VAS and Tolerability Scale are to be completed by the patient. Investigator to assess immediate and short term response.

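### The primary GAIS endpoint includes the grade of an investigator who cannot be blind, unranked beside the blinded evaluators' photographic grade

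*Protocol*

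**What the plan says.** Protocol section 2.1 describes the design: "This is a prospective, single centre, evaluator-blind study". Section 2.1.1 lists two primary endpoints, each at 12 and 16 weeks after treatment. One is the objective volumetric measurement with the Antera 3D system. The other is improvement in appearance against baseline, "as assessed by investigator and blinded evaluators by photographic assessment utilizing the Global Aesthetic Improvement Scale (GAIS").

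Section 2.1.2 places the other investigator-rated appearance scale among the secondary endpoints: improvement "compared to baseline as assessed by investigator utilizing the Modified Manchester Scar Scale (MSS").

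In section 4.3.2, the Visit 2 text (baseline and first treatment) reads: "The investigator will examine the treated areas and report immediate and short term response". For Visit 3 it reads: "Investigator to assess immediate and short term response", and Visits 4 and 5 carry the same instruction. Section 4.3.3 then has the investigator complete the GAIS and the Modified MSS at Visit 6 (12 weeks) and again at Visit 7 (16 weeks). Photographs are taken before the first treatment and at both follow-up visits.

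Section 3.1 continues enrolment "until 15 subjects have been treated according to the study protocol". No comparator is described.

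**The concern.** The GAIS is a judgement of how much better the treated skin looks than at baseline. Where every subject is treated and the comparison is before against after, a rater who knows that treatment was given and that the visit is a follow-up visit may expect improvement and grade accordingly. A control group would normally absorb part of that expectation, and none is described here. Blinded rating is therefore the main protection this endpoint has.

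Section 2.1.1 provides that protection for one kind of rater and then gives primary status to a second kind who does not have it. Nothing in the endpoint says which grade carries the result or how a disagreement is to be read. At stake is how the primary GAIS result can be interpreted: a favourable finding would rest partly on a grade that cannot be separated from rater expectation.

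**Working it through.** The protocol states no figure on this point that could be reproduced. The check is a comparison of sections, followed by a simple count.

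**1. Who rates the primary GAIS?** Section 2.1.1 names the investigator and the blinded evaluators, joined by *and*. The adjective *blinded* is attached only to the evaluators. No order of precedence is given.

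**2. Can the investigator be blind?** The protocol never calls the investigator unblinded, so this has to be inferred from the role:

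| Visit | Investigator's task (sections 4.3.2 and 4.3.3) |
|---|---|
| 2 (treatment 1) | Confirms eligibility, completes the baseline MSS, examines the treated areas, reports response |
| 3, 4, 5 (treatments 2 to 4) | Assesses immediate and short-term response |
| 6 (12 weeks) | Completes the GAIS and MSS |
| 7 (16 weeks) | Completes the GAIS and MSS |

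The role that grades improvement at Visits 6 and 7 has seen the treated skin at each treatment. A single treatment visit would be enough to remove any blinding. If a different person acted as investigator at follow-up, that person would still know that the visit falls after treatment.

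**3. Does the photographic wording change this?** The reference to photographic assessment in section 2.1.1 could grammatically cover both raters. Even so, an investigator grading from photographs at Visit 6 or 7 knows which visit it is and what was done.

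**4. Does the protocol treat investigator ratings consistently?** The MSS, rated by the investigator alone, is secondary in section 2.1.2. The investigator's GAIS, completed by the same role at the same two visits, is primary in section 2.1.1.

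**5. How much of the primary result is affected?** Counting each rater type at each time point as a separate result, which is one possible reading:

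- Antera: 1 measure × 2 time points = 2
- GAIS: 2 rater types × 2 time points = 4
- All primary results: 2 + 4 = 6
- Investigator's GAIS: 1 rater type × 2 time points = 2, which is 2 of 4 GAIS results and 2 of 6 primary results

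This count shows the place the investigator's grade holds among the primary results. It does not measure bias. The protocol gives no expected GAIS response and no expected disagreement between raters, so the size of any bias cannot be calculated.

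**The case against.** The strongest reply is that nothing here contradicts anything. Section 2.1 says that evaluators are blind, section 2.1.1 names blinded evaluators, and neither claims a blind investigator. That is correct. A reader might infer that the evaluator-blind label is false, and the text does not support this.

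A reader might also infer that the study could be declared positive on the investigator's GAIS alone, or that the two grades will be averaged. The protocol states no success rule and no pooling. Its wording can equally be read as requiring both grades or reporting both. How the two are summarised may be set out in a statistical analysis plan that is not at hand.

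A third tempting inference is that the blinded reading is not really planned, because the follow-up visit text mentions only the investigator's GAIS, or that it is inadequately masked, because photograph order is not addressed. Neither follows. Photographs are planned at baseline and at both follow-up visits, the schedule of events table is not shown, and masking of photograph order is reading detail that commonly sits in reading instructions or the analysis plan. Its absence here is not a protocol error.

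It is also fair to say that the Antera endpoint is objective and unaffected, and that a blinded GAIS is already primary.

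What remains is narrower. Whose grade defines a primary endpoint is a matter of endpoint definition, and section 2.1.1 has settled it by including the investigator. An analysis plan can describe how to summarise the two grades, but it would be working from a protocol that already makes both primary.

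**Conclusion.** The point holds as a weakness in how the primary GAIS endpoint is defined. An expectation-prone grade has primary status, unranked beside a blinded one, in a before/after study with no comparator described and a subjective scale. On the reading that counts rater types and time points separately, this concerns 2 of the 4 primary GAIS results and 2 of all 6 primary results. The effect on the reported improvement is unknown.

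The conclusion rests on two things: the inference from the visit schedule that the investigator knows treatment and time point, which is strong, and the absence of any ranking between the raters in the protocol text. It does not depend on how the grades would be combined. It is worth correcting because the correction is cheap and matches where the protocol already puts the investigator-rated MSS. It does not undermine the Antera endpoint or the blinded GAIS.

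**What to change.** In section 2.1.1, make the blinded evaluators' photographic GAIS at 12 and 16 weeks the only primary GAIS endpoint. Move the investigator's GAIS at the same time points to section 2.1.2 as a secondary endpoint beside the investigator-rated MSS, and state that it is reported separately and not pooled with the blinded grade. Make the change before the first Visit 6 GAIS is recorded, so that it cannot be influenced by results.

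The cost is protocol wording. No visit, photograph, rater or investigator assessment is added or removed. The downside is that the primary GAIS result may be less favourable than one that includes the investigator's grade.

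Optionally, the reading instructions or analysis plan could have evaluators read the baseline and follow-up photographs with dates and visit labels removed and in random order. That would need a rule for converting an order-masked judgement into a GAIS grade against baseline, and visible treatment marks could still partly unmask the readers. The endpoint change does not depend on this step.

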##### **2.1.2 SECONDARY PERFORMANCE ENDPOINTS**

- Improvement in the appearance of stretch marks at 12 weeks and 16 weeks post-treatment compared to baseline as assessed by investigator utilizing the Modified Manchester Scar Scale (MSS)
- Subjects' assessment of satisfaction with the treatment using a Subject Satisfaction Scale at 12 weeks and 16 weeks post-treatment.

##### **2.1.3 SAFETY ENDPOINTS**

- Subject's assessment of discomfort and pain after treatments as measured by a 10 cm visual analog scale (VAS) and Tolerability Scale
- Subjects experiencing a treatment-related adverse event (AE) by 16 weeks post-treatment.

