### **4.3.3 FOLLOW-UP**

#### **Visit 6 – 12 Week Follow Up Post Final Treatment (+/- 7 days)**

Subjects will return to the clinic 12 weeks after the final treatment. Adverse events, and any changes to concomitant medications will be recorded. Subjects will complete a Patient Satisfaction questionnaire. Investigator to complete a Global Aesthetic Improvement Scale (GAIS) and Modified MSS assessment. Photographs of the treated area will be taken.

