#### **Visit 7 – 16 Week Follow Up Post Final Treatment (+/- 7 days)**

Subjects will return to the clinic for a final study visit 16 weeks after the final treatment. Adverse events, and any changes to concomitant medications will be recorded. Subjects will complete a Patient Satisfaction questionnaire. Investigator to complete a GAIS and Modified MSS assessment.

Photographs of the treated area will be taken.

The termination form will be completed, and subjects will be terminated from the study. The PI will record all reportable events with start dates occurring any time after informed consent is obtained until 7 (for non-serious AEs) or 30 days (for SAEs) after the last day of study participation.

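### The only adverse-event endpoint counts treatment-related events alone, in a study with no described comparator and no stated rule for judging relatedness

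*Protocol*

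**What the plan says.** Section 1 of the protocol gives safety as one of the study's two aims. Section 2.1.3 lists two safety endpoints:

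- Subject-reported: "Subject's assessment of discomfort and pain after treatments as measured by a 10 cm visual analog scale (VAS) and Tolerability Scale".
- Adverse events: "Subjects experiencing a treatment-related adverse event (AE) by 16 weeks post-treatment".

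The second is the only endpoint built on adverse events. No endpoint for all adverse events, serious adverse events or events in the treated area is listed.

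Section 2.1 describes a single-centre, evaluator-blind study, and no control group appears anywhere in the visible text. Section 2.1.1 gives the blinded evaluators their task, which is improvement "as assessed by investigator and blinded evaluators by photographic assessment utilizing the Global Aesthetic Improvement Scale (GAIS"). They have no stated role in adverse events.

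Collection is broader than the endpoint. Adverse events are listed at Visits 3 to 5 (section 4.3.2) and at Visits 6 and 7 (section 4.3.3) without restriction to related ones. The Visit 6 text reads: "Adverse events, and any changes to concomitant medications will be recorded". The Visit 7 text adds: "The PI will record all reportable events with start dates occurring any time after informed consent is obtained". Relatedness is mentioned only in section 2.1.3.

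**The concern.** The endpoint applies a causality filter before anything is counted. In a controlled trial, errors in that filter would at least fall on both arms and could be compared. Here there is no described comparator, blinding does not extend to causality, and neither the assessor nor the criteria are given.

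A skin reaction at the treated site has plausible alternative explanations. The protocol itself supplies one, since section 4.3.2 allows a topical anesthetic on the treatment site before treatment. A reaction attributed to the anesthetic would be recorded, yet it need not appear in the endpoint. If section 2.1.3 is followed as written, the reader of the result sees only events that passed an unspecified judgement and cannot tell how many did not.

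**Working it through.** The protocol gives no adverse-event rate, precision target or sample-size derivation, so there is no figure of its own to reproduce. The check has three parts.

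**1. Endpoint set against data capture**

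| Item | Where | Relatedness filter? |
|---|---|---|
| Adverse-event endpoint | 2.1.3 | Yes |
| Adverse events at Visits 3 to 5 | 4.3.2 | No |
| Adverse events at Visits 6 and 7 | 4.3.3 | No |
| Recording rule from consent onward | 4.3.3, Visit 7 | None stated (which events are reportable is not defined) |
| Who assigns relatedness, and how | Not in the visible text | n/a |

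The restriction lies in the endpoint and not in what is collected.

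**2. Direction of the error**

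Let T be the number of subjects with a truly related event, m the number of these whose events are all called unrelated, and f the number with only unrelated events of which at least one is called related. Then

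observed related count = T − m + f.

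This can fall below T or rise above it. Against the count A of subjects with any event, however, the related count can never exceed A, so the filter can only subtract from the all-cause figure.

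**3. Size with n = 15**

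Input: n = 15, from section 3.1 ("until 15 subjects have been treated according to the study protocol"). Using 15 as the safety denominator is an assumption.

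Step per reclassified subject: 1/15 = 6.7 percentage points.

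Exact (Clopper-Pearson) two-sided 95% limits for x of n subjects:

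- lower = 2.5% quantile of Beta(x, n − x + 1), and 0 when x = 0
- upper = 97.5% quantile of Beta(x + 1, n − x)

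Check for x = 0: upper = 1 − 0.025^(1/15) = 0.218.

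| Subjects counted | Rate | Exact 95% limits |
|---|---|---|
| 0/15 | 0% | 0 to 21.8% |
| 1/15 | 6.7% | 0.2 to 31.9% |
| 2/15 | 13.3% | 1.7 to 40.5% |
| 3/15 | 20.0% | 4.3 to 48.1% |

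For illustration, assume that three subjects have an event in treated skin. Depending only on attribution, the endpoint can be reported as anything from 3/15 to 0/15, the full span of the table. The figure of three is an assumption; the protocol gives no expected rate.

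**The case against.** The strongest reply is that nothing in section 2.1.3 is false or contradicted elsewhere. Events are collected whatever their cause, and full adverse-event tables with exact limits commonly belong in a statistical analysis plan, which may exist. The visible protocol may also be incomplete: section numbering passes from 4.1.2 to 4.3, and a Schedule of Events Table is mentioned but not shown. Causality procedures might therefore have stood elsewhere.

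Part of this stands. No data are lost, and a missing table is not the complaint. But the endpoint is defined in the protocol, and an analysis plan that implements it faithfully would count related events only, with all-cause counts as a supplement at best.

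Four stronger readings may tempt a reader, and the document does not support them:

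- *One unblinded treating investigator decides causality.* This is plausible at a single centre where the principal investigator records events, but the protocol does not say who judges relatedness or how many people do. The documented gap is that this is unspecified.
- *The whole safety result rests on that judgement.* It does not. The pain VAS and Tolerability Scale need no attribution. The investigator also examines treated areas 20 to 30 minutes after treatment on a 5-point scale (section 4.3.2), although that early assessment is not a listed safety endpoint.
- *Misattribution can only lower the rate.* That holds against the all-event count but not against the truly related rate.
- *Counting all events removes judgement.* Someone must still decide what is an adverse event and whether it lies in a treated area, and section 4.1.2 allows several areas per subject. The change removes the causality step only.

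**Conclusion.** The point holds in a limited form. The one adverse-event endpoint depends on an attribution whose assessor and criteria the visible text does not give, with no described comparator and no blinding to check it. Each reclassified subject moves the rate by 6.7 percentage points, in either direction relative to the truly related rate. Over the small counts tabulated above, the exact upper limit runs from 21.8% to 48.1%.

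This rests on three assumptions: that 15 is the safety denominator; that the undefined term for reportable events does not itself exclude unrelated ones, as the unrestricted visit texts suggest; and that no causality procedure stood in text that is not visible. How many events would be attributed elsewhere cannot be estimated from the protocol. The study remains interpretable without the change, but the change is worth making because it is cheap and the events are already recorded.

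**What to change.** Reword the second safety endpoint in section 2.1.3 along these lines:

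*Subjects with any adverse event, and subjects with any adverse event in a treated area, regardless of attributed cause, from first treatment to 16 weeks post-final treatment, with treatment-related events reported as a subset.*

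Report each as a count with exact 95% limits. Because the related subset is kept, add a sentence saying who judges relatedness and by what criteria.

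The cost is a sentence or two in the protocol and one more table row, with no new visit or procedure. The downside is that the headline rate will include some unrelated events and may look less favourable. Showing the related subset beside it lets the reader see how much of the difference is attribution.
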